STUDY SYNOPSIS**NCT03926819****Date: January 30, 2023**

Title of Study: A Phase 1 ascending single-dose followed by multiple dose safety and pharmacokinetic study of HBI-002 carbon monoxide liquid formulation in healthy adult volunteers.
Protocol Number: HBI-002-001
Investigators/Study Center:
Phase of Development: 1
Objectives/Endpoints: Primary Objective/Endpoint: To assess the safety and tolerability of HBI-002, given as single ascending doses (SAD) and multiple doses (MD) daily for 7 days in healthy male and female adult subjects based on frequency and severity of TEAE, including adverse events of special interest. Secondary Objectives/Endpoints: 
1. To evaluate the pharmacokinetics (PK) of HBI-002 with increasing doses of oral HBI-002 as measured by COHb levels.2. To determine the HBI-002 dose required to achieve peak COHb levels up to 10% within one hour after ingestion.3. To evaluate any accumulation of CO as measured by COHb with daily dosing and to assess changes in venous lactate levels.4. To evaluate biomarkers of inflammation and to assess changes induced by HBI-002.
Planned Sample Size: Up to 16 subjects will be enrolled in the SAD phase (up to 4 dose cohorts) and 4 subjects in the MD phase (one dose cohort). Additional subjects (up to 8 in the SAD phase and up to 6 in the MD phase) may be enrolled in any cohort, as needed, if incomplete data is obtained or there is a need to obtain additional safety observations. Subjects in the MD cohort will be replaced if all 7 doses are not ingested or labs for safety assessment are not complete. Subjects will not be replaced in the event the subject discontinues the study due to a related adverse event.
Study Duration: Approximately 26 weeks

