Study Design: This is a single center, open-label trial investigating up to four single ascending doses (SAD), followed by a single cohort of multiple doses (MD) with dosing daily for 7 days. Both the SAD and MD dosing cohorts utilize an adaptive dosing regimen. Eligible healthy adult subjects who have signed the informed consent will undergo a screening assessment carried out within 4 weeks of study entry consisting of a medical history, concomitant medications, physical examination, height and weight, vital signs, ECG, hematology and chemistry labs, infectious disease screen including SARS-CoV-2, hemoglobin electrophoresis, urinalysis, pregnancy and drug screen. Pregnancy testing in females of childbearing potential will be carried out in both the SAD and MD study components at screening and baseline, as well as in the SAD component at 48 hours and on Day 30, and in the MD component on Days 8 and 37. Concomitant medications and adverse events will continue to be monitored to the final follow up visit.
Dosing rules (SAD and MD) For the SAD study component, there will be at least 72 hours between dosing of the first study subject at each dose level and the subsequent 3 subjects at the same dose level and with no minimum time between dosing of each subsequent subject. There also will be at least 72 hours between the last subject at each dosing level and the first subject at the next dose level. For the MD study component,

there will be at least 30 days between the last subject at the final SAD dose level and the first subject in the MD dose level. For the MD dosing, there will be 72 hours between the first subject receiving the first MD dose and the subsequent 3 subjects at that dose level with no minimum time between dosing of the 3 subsequent subjects.

All subjects (SAD and MD)

Peak COHb measured by co-oximeter will be monitored for safety, targeting levels of no more than 10% COHb, and COHb saturation will be documented for each subject at all time points. The DSMB will review safety information through 72 hours after completion of dosing for each SAD cohort. The specific dose cohort at the next level, as designated under SAD dosing, may proceed provided that no related safety issues are observed.

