 - b. liver function: alanine transaminase (ALT) and aspartate transaminase (AST) ≤ 2 times the upper limit of the normal range

- c. total bilirubin \leq 1.5 times the upper limit of the normal range
- d. renal function: creatinine clearance within normal range as assessed by Cockcroft and Gault calculation
- e. carboxyhemoglobin level by venous blood gas \leq 3.5% (any time prior to the first dose)
- f. venous lactate level $<$ 2.0 mmol/L at baseline.
- g. the absence of current clinically relevant abnormalities identified by a detailed medical history, full physical examination including blood pressure and pulse rate measurement, 12-lead ECG, and clinical laboratory tests (hematology and clinical chemistries), as determined by the Investigator.

7. Negative pregnancy tests for females.
8. Subjects must be willing to use a highly effective method of contraception for the duration of the study and for 30 days thereafter.
 - a. Male subjects, without a vasectomy, must use a condom and be instructed that their female partner should use another form of contraception such as an IUD, diaphragm with spermicide, oral contraceptive, injectable progesterone, subdermal implant or a tubal ligation if the female partner could become pregnant
 - b. Female subjects of childbearing potential (not surgically sterilized and less than one year post-menopausal) should use a form of contraception such as an IUD, diaphragm with spermicide, oral contraceptive, injectable progesterone, subdermal implant or a tubal ligation, and be instructed that their male partners should use a condom, if not vasectomized.

Exclusion Criteria

Subjects who meet any of the following criteria will be ineligible for participation in the study:

1. Subjects with concurrent illness/disease as defined by:
 - a. clinically significant hematological, renal, endocrine, pulmonary, gastrointestinal, cardiovascular, hepatic, psychiatric, neurologic or allergic disease, as determined by the Investigator.
 - b. current clinically relevant abnormalities identified by a detailed medical history, full physical examination including blood pressure and pulse rate measurement, 12-lead ECG, and clinical laboratory tests (hematology, clinical chemistries and urinalysis), as determined by the Investigator.
 - c. clinically significant illness and/or surgery within 4 weeks prior to dosing.
2. Anemia of any cause.
3. Homozygous or heterozygous hemoglobinopathy.

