Criteria for Evaluation/Statistical Methods:**Pharmacokinetics:**

PK will be assessed in each subject based on whole blood COHb levels obtained at each designated blood draw. PK will be assessed on each subject in the SAD phase and on each subject in the MD phase with COHb. In the MD phase, PK analysis will be carried out on both the first and final dose of HBI-002. Standard pharmacokinetic parameters for COHb incremental recovery [IR], maximum concentration following oral administration [Cmax], time to reach Cmax [Tmax], terminal or disposition half-life [$t_{1/2}$], mean residence time [MRT], systemic clearance [Cl/F], area under the whole blood-time curve [AUC] and volume of distribution [Vd/F] after single oral administrations of HBI-002 at each dose level. The PK concentration data at each timepoint will be listed for each subject and summarized by dose level using descriptive statistics. Individual subject and mean concentration-time data will be graphically presented separately. If sufficient data are available across SAD dose cohorts, dose proportionality will be evaluated using a power model.

PK analyses will use the actual observed sample drawing times. Samples with unknown drawing time and/or where the concentration could not be determined will be eliminated from the calculations. Concentration data will be carried out in two modes: No correction for baseline value and corrected for baseline by subtraction of the mean pre-dosing value.

PK parameters will be derived using noncompartmental methods with appropriate software. The following parameters will be calculated for each patient separately: AUC, IR, Cmax, AUCinf, Tmax, $t_{1/2}$, MRT, Clearance (CL/F) and Vd/F. These parameters will be summarized for each Dose Cohort separately by using descriptive statistics (number, mean, standard deviation, minimum, maximum, median, coefficient of variation, geometric mean and the corresponding 90% confidence intervals as appropriate).

Safety:

All safety data will be included in the subject data listings. Summary tables will be based upon the safety population.

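### Could the unspecified pre-dose baseline for COHb hide accumulation over the seven daily doses?

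*Combined protocol and SAP*

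**What the plan says.** Secondary objective 3 (synopsis, Objectives/Endpoints) is "To evaluate any accumulation of CO as measured by COHb with daily dosing", together with changes in venous lactate. The MD phase plans "4 subjects in the MD phase (one dose cohort"), dosed daily for 7 days.

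The section Criteria for Evaluation/Statistical Methods, Pharmacokinetics, states: "In the MD phase, PK analysis will be carried out on both the first and final dose of HBI-002". COHb is handled in two modes, one without correction and one "corrected for baseline by subtraction of the mean pre-dosing value". A first list of parameters is described as obtained "after single oral administrations of HBI-002 at each dose level". A second list (AUC, IR, Cmax, AUCinf, Tmax, half-life, MRT, CL/F, Vd/F) is calculated per subject and has no such restriction. Of these the plan says: "These parameters will be summarized for each Dose Cohort separately by using descriptive statistics". COHb at each timepoint is listed by subject, and individual curves are plotted.

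No accumulation ratio, pre-dose comparison or final-versus-first contrast is named. The plan does not say which dose the pre-dosing value precedes. The phrase "any time prior to the first dose" is attached to COHb only in the eligibility criteria (Inclusion 6e and Exclusion 5).

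**The concern.** Each MD subject contributes two PK profiles, so the pre-dosing value can be read in two ways.

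- **Reading (a):** the subject's COHb before the first MD dose, subtracted from both profiles. Only the endogenous level is removed.
- **Reading (b):** each profile's own pre-dose value. For the final dose this includes COHb left from six earlier doses, which is what objective 3 asks about. The subtraction also over-corrects later samples, because the carry-over decays during the interval while the subtracted value stays constant.

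Under (b), corrected Cmax would look flat and corrected AUC would fall although exposure had risen. The two planned modes would then disagree in direction, with no rule saying which one answers the objective. With four planned MD subjects, a choice made after seeing the data could decide what is reported.

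**Working it through.** The plan gives no accumulation figure to reproduce, so the check asks how far reading (b) could mislead and what the rest of the plan would still show.

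**Inputs from the documents:** 7 daily doses (24 h interval); peak COHb target of no more than 10%; COHb eligibility limit of 3.5%.

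**Assumptions:** bolus input, mono-exponential decay, equal doses, half-life 3 to 12 h, endogenous COHb 1% or 3.5%, total first-dose peak 10%.

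**Formulas**, with k = ln 2 / half-life and amounts in units of the first-dose peak increment:

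- True final/first ratio: R = sum over i = 0 to 6 of exp(-24ki). Carry-over before dose 7: c = R - 1.
- A = (1 - exp(-24k))/k, the first-dose AUC0-24.
- Reading (a): Cmax and AUC ratios both equal R.
- Reading (b): Cmax ratio = R - c = 1; AUC0-24 ratio = R - 24c/A.
- Uncorrected, endogenous level b: AUC0-24 ratio = [(10 - b)RA + 24b] / [(10 - b)A + 24b].

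**Worked case, 8 h:** k = 0.0866; R = 1.143; c = 0.143; A = 10.10. Reading (b) AUC ratio = 1.143 - 0.143 × 24/10.10 = 1.143 - 0.339 = 0.80. Uncorrected with b = 1: (9 × 1.143 × 10.10 + 24)/(9 × 10.10 + 24) = 1.11.

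| Half-life (h) | True ratio, reading (a) | (b) Cmax | (b) AUC0-24 | Uncorrected AUC0-24, b = 1% | Uncorrected AUC0-24, b = 3.5% |
|---|---|---|---|---|---|
| 3 | 1.00 | 1.00 | 0.98 | 1.00 | 1.00 |
| 4 | 1.02 | 1.00 | 0.95 | 1.01 | 1.01 |
| 6 | 1.07 | 1.00 | 0.87 | 1.05 | 1.03 |
| 8 | 1.14 | 1.00 | 0.80 | 1.11 | 1.06 |
| 12 | 1.33 | 1.00 | 0.72 | 1.28 | 1.17 |

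A separate calculation with first-order absorption (4 per hour), endogenous 1% and a peak increment of 8% gave reading (b) AUC ratios of 0.98, 0.80 and 0.71 at 3, 8 and 12 h. The bolus simplification does not drive the result.

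**Which reading the text favours.** The correction is expressly for baseline. In Study Design, baseline is an assessment next to screening and distinct from MD Days 8 and 37. Inclusion 6f sets a lactate limit at baseline, and Exclusion 21 refers to screening and/or baseline. In that usage a sample before the seventh dose is not baseline, so reading (a) is the natural one, and it returns the true ratio.

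**What survives under reading (b).**

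- The uncorrected mode never points the wrong way. The share of the AUC increase it shows is (uncorrected ratio - 1)/(R - 1): 75% to 83% for b = 1% and 39% to 50% for b = 3.5%, at half-lives of 6 to 12 h.
- Reading (b) can be applied only if a sample was taken before the final dose. That value is then in the subject's listing, and its difference from the value before the first dose is the carry-over itself: with b = 1% and 8 h, 9 × 0.143 = 1.3 percentage points.
- The Safety section lists any COHb above 10% separately, regardless of baseline correction. With b = 1%, the final-dose peak would be 9R + 1 = 10.6%, 11.3% and 13.0% at 6, 8 and 12 h.

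**The case for a change.** The best case for a change is that a stated secondary objective has no named measure, while dose proportionality gets a power model. The eligibility wording about the first dose screens subjects and does not define a PK baseline. A short half-life does not remove the point: at 4 h the error under reading (b) (-5%) exceeds the true effect (+2%) and has the opposite sign. If every subject sat at the 3.5% limit, the uncorrected mode would show about half or less of the AUC increase.

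The arithmetic stands, and so does the observation that the text is silent. But the distortion needs the less natural reading, and it is material only at longer half-lives, which the documents neither support nor exclude. The 50% dilution needs all subjects at the eligibility ceiling. No data are lost: with four subjects and both profiles listed, the final/first ratios can be formed in minutes on either baseline, and opposite signs in the two modes would prompt exactly that. The reference to single administrations sits in a sentence without a main verb, and the later, operative list carries no such limit.

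Two side issues add no weight. The plan does not say which AUC a final-dose CL/F would use, so no wrong rule is stated. The sentence "Both the SAD and MD dosing cohorts utilize an adaptive dosing regimen" can stand beside a single MD cohort; if first and final doses did differ, dose-normalising the ratio is routine.

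**Conclusion.** No change follows. The plan leaves a term undefined and a summary unnamed; it does not prescribe a calculation that gives a wrong answer. Under the reading that the synopsis's own use of baseline favours, the correction is sound and returns the true ratio. Under the other reading the corrected AUC0-24 ratio would be 0.98 to 0.72 against a true 1.00 to 1.33, for half-lives of 3 to 12 h. Even then the uncorrected mode, the two MD profiles and the listings keep objective 3 answerable in a descriptive four-subject cohort.

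These sizes rest on a one-compartment linear model and on half-lives that the documents do not give. At about 4 h or less the reading (b) ratio is 0.95 to 0.98 against a true 1.00 to 1.02, of little consequence here. The text available is a synopsis without the MD sampling schedule, so a fuller definition may exist elsewhere. An analyst would be expected to use the value before the first MD dose for both profiles and to report a final/first comparison.

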Serious and non-serious adverse events, occurring up to 30 days after the last oral dose will be tabulated and summarized according to the most recent version of the MedDRA. Frequencies and percentages of subjects experiencing at least one event will be summarized by system organ class and preferred term for all AEs, for AEs considered to be possibly or probably related to the study drug, and for SAEs. The number and proportion of subjects experiencing these events will be tabulated by dose for each study phase (SAD or MD). Related adverse events will be listed.

Individual and summary vital signs and clinical laboratory data will be presented for each study phase in tabular form with mean, standard deviation and range as appropriate.

For the vital signs, transcutaneous oxygen concentration, venous COHb and other laboratory safety data, and ECG data, out of range values considered to be clinically significant will be flagged in the data listings and a separate listing of clinically significant abnormal values will be presented, including any COHb value >10%.

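### Do the planned adverse-event tables leave out the severity, special-interest and treatment-emergent parts of the primary endpoint?

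*Combined protocol and SAP*

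**What the plan says.** Under Objectives/Endpoints, the primary objective is safety and tolerability of single and multiple doses, "based on frequency and severity of TEAE, including adverse events of special interest". Four elements are named: frequency, severity, treatment-emergent status and special interest.

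The Safety part of Criteria for Evaluation/Statistical Methods sets out the reporting:

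- **Window.** "Serious and non-serious adverse events, occurring up to 30 days after the last oral dose will be tabulated". An end is given, but no start.
- **Tables.** Each table gives counts and percentages of the subjects affected. These "will be summarized by system organ class and preferred term for all AEs, for AEs considered to be possibly or probably related"; a third set covers serious events. Each is split by dose within the single-dose and multiple-dose phases.
- **Listings.** "All safety data will be included in the subject data listings", and "Related adverse events will be listed". A separate listing covers out-of-range values judged clinically significant, with every COHb value above 10%.

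Under Study Design, after the description of screening, the text adds: "Concomitant medications and adverse events will continue to be monitored to the final follow up visit". It does not say when recording begins.

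**The concern.** Set against the endpoint, the three named tables deliver frequency and nothing else explicitly. Seriousness is tabulated, but seriousness is not severity. In the supplied text the terms for treatment-emergent events, severity and special interest each occur once, all in the primary objective. No grading scale, list of special-interest terms or definition of treatment emergence follows.

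In a dose-escalation study whose main question is tolerability by dose, this could matter in two ways. First, a dose with only mild events and a dose with only severe but non-serious events, of the same terms and relatedness, would give identical rows. Second, screening may run up to 4 weeks before study entry. If events are recorded from then, an event before dosing could be counted against a dose cohort.

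**Working it through.** The plan states no figure to reproduce, and no test, power or alpha is involved. The check sets each endpoint element against the outputs named under Safety.

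| Endpoint element | Named summary table | Other named output |
|---|---|---|
| Frequency | Yes: all, related and serious AEs, by dose and phase | Listings |
| Severity | None named | Subject listings of all safety data |
| Special interest | No dedicated table; counted by preferred term in the all-AE table | Subject listings; COHb values above 10% listed separately |
| Treatment-emergent | End of window given, start not given | Subject listings |

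**Severity.** This is the one element with no named table at all. To size what a frequency row conceals, assume three grades (the text gives no scale). Take one non-serious term with k subjects affected. The number of possible maximum-severity patterns is C(k+2, 2):

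- k = 1: C(3,2) = 3
- k = 2: C(4,2) = 6
- k = 3: C(5,2) = 10
- k = 4: C(6,2) = 15

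These count possibilities. They do not show that any conclusion would change.

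**How much reading the listings require.** From Planned Sample Size: 16 + 4 = 20 subjects planned, and 20 + 8 + 6 = 34 with all additional subjects. Sixteen subjects over four single-dose cohorts is 16/4 = 4 each, and the multiple-dose cohort is also 4. If every additional subject in a phase went into one cohort, it would reach 4 + 8 = 12 (single dose) or 4 + 6 = 10 (multiple dose). Listings of that size can be read in full.

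**Special interest.** The endpoint wording includes these events within the treatment-emergent events. The all-AE table therefore counts each of them under its preferred term, by dose and phase. What is missing is a dedicated table, and the endpoint does not ask for one.

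**Treatment-emergent.** If recording starts at first dose, the stated window is already the treatment-emergent window and nothing changes. If it starts at screening, each subject whose only event is before dosing adds one to the all-AE count, so a cohort of 4 goes from 0/4 (0%) to 1/4 (25%). No rate of pre-dose events is given, so no expected bias can be calculated. The related-event table should in practice be unaffected, since an event before dosing would not be attributed to study drug.

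**Completeness of the text.** The document is headed as a synopsis and points to content that does not appear in it. The Stopping Rules refer to a list of signs and symptoms of CO toxicity further on. The paragraph for all subjects refers to dose levels set out under single-dose dosing. Neither is in the supplied text. Missing definitions of severity grade or special-interest terms are therefore weak evidence that the trial has none.

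**The case for a change.** The strongest case for a change is this. The Statistical Methods section is specific: it names its tables, and none is by severity, although severity is half of the primary endpoint. A listing is not a summary by dose. Small cohorts do not excuse the omission, because the plan tabulates frequency in those same cohorts. Restricting the tables to the safety population selects subjects, not event dates, so it does not remove pre-dose events. The trial is open-label, so a grading scale or special-interest list not fixed in advance could be chosen with the data in view. The remedy would be cheap: two tables and three definitions, with no extra subjects or visits.

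Some of this stands. No severity table is named, the start of the window is unstated, and listings are a weaker form of reporting than a table. The rest does not carry. Nothing in the Safety section forbids or contradicts a severity summary, and the primary objective requires severity to be reported. An analyst who worked from these tables alone would not have reported the stated endpoint, and would know it. The worry about choosing definitions late rests on their absence from a synopsis that visibly omits other material. Escalation depends on data safety monitoring board review after each single-dose cohort and on the stopping rules, so the omitted tables would not steer dosing.

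**Conclusion.** The observation is accurate but narrow: the Safety section names no summary by severity and gives no start to the event window. It is not accurate to say that the tables miss the primary endpoint, since frequency is fully tabulated and special-interest events are counted within all AEs.

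No change to the plan follows. The gap is one of detail. The endpoint already commits the analysts to severity and to treatment-emergent events, and the usual practice of tabulating by maximum severity and counting from first dose fits everything written here. No stated rule has been shown to give a wrong result.

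The practical size is small: 20 planned subjects (34 at most), cohorts planned at 4, full listings and no hypothesis test. The worst identifiable effect on a count is one subject in a cohort of 4 for each subject with only a pre-dose event, and only if recording begins before dosing.

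This rests on two assumptions: that a severity grade is recorded for each event, as the endpoint requires, and that onset dates are recorded, so that events before dosing can be separated. If either failed, the listings could not fill the gap and the matter would need to be reopened.
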